E.1 RISK TO THE SUBJECTS

E.1.a Human Subject Involvement and Characteristics

We plan to recruit a total of 30 individuals (male, female; age range 18-85 years) referred to undergo a clinically indicated PET-CT examination. Patients will be identified from the Radiology department schedule. Study eligibility determination and study enrollment will be assessed and performed by a physician who is a principle investigator or a sub-investigator, as recorded with the IRB as being authorized to obtain informed consent. In the absence of exclusion criteria the responsible physician of record will be contacted, the study will be discussed and permission (or not) to approach the patient will be sought. At this time the potential use of beta-blockers will be discussed with the responsible physician of record, potential contraindications will be ruled out and permission to approach the patient for beta-blocker administration will be sought. The patient will be approached by IRB-approved study personnel under the direction of one of the licensed physician investigators listed on the study, either prior to or on the day of the planned PET-CT examination, with a full explanation and request for consent as required by the IRB. Emory policies regarding patient consent will be followed. The study design is not randomized.

Inclusion Criteria:

To be eligible for the study: (All answers must be “**YES**”, for subject to be eligible.)

1. Subject must be referred for a clinically indicated CT-MPI for CAD assessment.
2. Subject must be 18 – 85 years of age.
3. Subject must provide written informed consent prior to any study-related procedures being performed.
4. Subject must be willing to comply with all clinical study procedures.

Exclusion Criteria:

The presence of the following excludes subjects from the study: (All answers must be “**NO**” for subject to be eligible.)

1. Subject is a pregnant or nursing female. Exclude the possibility of pregnancy:
 - By testing (serum or urine β HCG) within 24 hours before study agent administration, or
 - By surgical sterilization, or
 - Post menopausal, with minimum one (1) year history without menses.
2. Subject is currently taking or has taken within 48 hours the following excluded medications:

ActoPlus Met (Pioglitazone + metformin)

Avandamet (Rosiglitazone + metformin)

Fortamet (metformin)

Glucovance (Glyburide +metformin)

Glucophage (metformin)

Glucophage XR (metformin)

Glumetza (metformin)

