Janumet (Sitagliptin + metformin)

Metformin (metformin)

Metaglip (Glipizide + metformin)

Riomet (metformin)

3. Subject has an acute psychiatric disorder.
4. Subject is unwilling to comply with the requirements of the protocol.
5. Subject has previously entered this study.
6. Subject with known hypersensitivity to iodinated contrast material, beta-blockers, or pharmaceutical stressors used in this study.
7. Subject suffers from claustrophobia.
8. Subject has impaired renal function (GFR < 45 ml/min).
9. Acute hypotension (<100 mm Hg systolic).
10. Subject with 2nd or 3rd degree AV block.

Patients with heart rates >75 bpm will receive β -blockers in order to level-down the heart rate.

Patients with contraindications to the use of beta-blockers (chronic obstructive pulmonary disease, asthma sensitive to beta agonists, second- or third-degree heart block, hypotension (<100 mm Hg systolic) are in principle eligible for participation in the study, however, no beta-blockers will be used in such individuals. There will not be any eligibility criteria for any subpopulations. In addition, there will not be any involvement of special classes of subjects, such as fetuses, neonates, pregnant women, children, prisoners, institutionalized individuals, or others who may be considered vulnerable populations. All race and ethnicities and both genders will be considered for inclusion into the study. Subjects under the age of 18 will not be considered for inclusion into this study. This research will only be conducted at the Emory University.

E.1.b Sources of Materials

The research materials that will be obtained from living human subjects are: the cardiac CT-MPI, PET-MPI and all applicable other imaging studies (e.g. echocardiography), progress notes, medication records, vital signs, medical history and demographics and all other applicable clinical information.

The Principle Investigator, Sub-Investigator(s) and the Study Coordinator(s) will be the only personnel who will have access to subject identities, with the exception of any regulatory personnel (Emory IRB auditors, etc.). All subject identities will be removed prior to publication.

E.1.c Potential Risks

Patient discomfort

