Subjects will be monitored in clinic as per clinical standard practice for any possible side effects and treated as indicated.

E.3 POTENTIAL BENEFITS OF THE PROPOSED RESEARCH TO THE SUBJECTS AND OTHERS

Since the CT examinations in this study are performed for research purposes and are not used for diagnostic purposes, there are no direct benefits for study participants. However, the knowledge gained from this study may benefit future patients undergoing CT-MPI and CT-FFR.

Compensation to Participants

Participants will be compensated with a \$200.00 gift card to cover for parking, travel costs etc.

E.4 IMPORTANCE OF THE KNOWLEDGE TO BE GAINED

Knowledge gained during this study will enable an appreciation of the diagnostic accuracy of CT-MPI and CT-FFR in comparison to PET-MPI for diagnosis of coronary artery disease and give indications of potential impacts on clinical and diagnostic pathways. Furthermore, the diagnostic value of cardiac CT imaging in detection coronary stenosis may be improved.

E.5 SUBJECT SAFETY AND MINIMIZING RISKS (Data and Safety Monitoring Plan)

Eligibility in each case will be confirmed by a named investigator. The source data will be collected by an independent technician and/or study coordinator, maintained securely by the PI and checked by the named investigators. Clinical data will be recorded on a Case Report Form (CRF). However, formal monitoring of site records will not be completed as part of the general conduct of the study. Data collected will be authentic, accurate and complete and the study will be conducted in accordance with the currently approved protocol (and any future approved amendments), Good Clinical Practiced (GCP) and all applicable regulatory requirements.

Any event meeting the criteria of an unanticipated problem involving risks to subjects or others will be reported to the Emory IRB, as required by HRPP 4.7- Unanticipated Problems and Adverse Events Policy and Procedures. Clinical data will not be monitored by a 3rd party (i.e. Clinical Research Associate (CRA)) or sponsor but the results of the study will be written up as a paper and may be submitted as abstracts to various conferences. Every effort will be made to ensure patient safety and confidentiality.

F. ADDITIONAL MATERIAL

PET MPI Clinical Protocol

PROCEDURE TITLE: Rubidium PET Myocardial Perfusion Imaging

APPLICABLE FACILITIES: (Check all that apply)

EUH EUOSH EWWH EUHM EJCH ESJH TEC ESA ERH

EFFECTIVE DATE: 1/9/2019

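### E.1.a contradicts itself on second- and third-degree heart block, and its first inclusion criterion names the wrong referral test

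*Combined protocol and SAP*

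**What the plan says.** Section E.1.a gives a headed list of four inclusion items, all of which must be answered yes, and ten exclusion items, all of which must be answered no. Exclusion 10 is "Subject with 2nd or 3rd degree AV block". Exclusion 9 is "Acute hypotension (<100 mm Hg systolic".

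The text directly below the list sets a heart-rate rule: "Patients with heart rates >75 bpm will receive" beta-blockers. It then names four contraindications to beta-blockers: COPD, asthma sensitive to beta agonists, heart block and hypotension. Of these patients it says that those with "second- or third-degree heart block, hypotension (<100 mm Hg systolic) are in principle eligible for participation in the study", and adds "however, no beta-blockers will be used in such individuals".

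Inclusion 1 requires that the patient be referred for a clinical CT-MPI. Elsewhere (D.1, the opening of E.1.a, and E.2.a) patients come to the study through a clinical PET referral, and E.3 states that the CT is done for research and not for diagnosis.

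D.1 also excludes patients with an earlier cardiac intervention, giving PCI and CABG as examples. The E.1.a list has no such item.

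**The concern.** Exclusion 10 and the beta-blocker sentence give opposite answers for the same condition in the same section, and no rule says which text prevails. The sentence also tells staff how to treat such patients once they are in the study, which presupposes that they take part.

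This matters more for heart block than it would for most criteria. The CT-MPI is a pharmacological stress test with no direct benefit to the participant (E.3). Regadenoson is the preferred agent (D.1), and E.1.c lists AV nodal block among its warnings. The people who check eligibility work from this text, and E.5 plans neither formal monitoring of site records nor third-party review of clinical data that might catch a misreading.

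Inclusion 1 has a different effect. Because it must be answered yes, a literal screener would turn away the patients the study is meant to recruit.

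**Working it through.** No sample-size, power or error-rate figure bears on this point, so there is nothing numerical to reproduce. The check sets the eligibility statements side by side.

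**Step 1. The four conditions in the beta-blocker sentence against the ten exclusion items**

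| Condition in the sentence | Matching exclusion item | Result |
|---|---|---|
| COPD | none | no conflict |
| Asthma sensitive to beta agonists | none | no conflict |
| Second- or third-degree heart block | item 10, same condition | direct contradiction |
| Hypotension, systolic <100 mm Hg | item 9, same threshold, qualified as acute | overlap; extent depends on the meaning of acute |

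Of the ten exclusion items, 1 is contradicted outright (item 10), 1 overlaps (item 9), and 10 − 1 − 1 = 8 are untouched by the sentence.

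**Step 2. Hypotension**

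The threshold is identical in both places, and the only difference is the word acute, which the protocol does not define. There are two readings:

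- If acute adds nothing, item 9 and the sentence contradict each other just as item 10 does.
- If acute limits item 9, patients with longer-standing systolic pressure below 100 mm Hg are eligible and the sentence tells staff to withhold beta-blockers from them.

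The documents do not settle which is meant. Hypotension is also among the regadenoson warnings in E.1.c, so the choice is a clinical one for the sponsor.

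**Step 3. Referral test**

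- Clinical CT-MPI: 1 statement (inclusion 1).
- Clinical PET: 4 statements (the opening of D.1, the PET-MPI Protocol paragraph of D.1, the opening of E.1.a, and E.2.a).
- E.3 makes the CT research-only, so the study design provides no clinical CT-MPI referral for inclusion 1 to refer to.

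The intended test is therefore PET-MPI.

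**Step 4. Prior intervention**

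D.1 excludes it, and 0 of the 10 items in the E.1.a list name it. E.2.a screens on the criteria listed earlier. That most naturally means the headed list in E.1.a, although D.1 also comes before E.2.a. This is an omission from the list, not a contradiction.

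**Step 5. Number of patients affected**

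The documents give no rate of heart block, hypotension or prior revascularisation among the referred patients, so the number affected among the 30 cannot be estimated.

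**The case against.** The strongest reply is that the all-no rule makes exclusion 10 operative, and that the later sentence is softly worded and concerns beta-blocker handling. Several checks support this:

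- E.1.a: "Study eligibility determination and study enrollment will be assessed and performed by a physician who is a principle investigator or a sub-investigator".
- E.1.a: "In the absence of exclusion criteria the responsible physician of record will be contacted".
- E.5: "Eligibility in each case will be confirmed by a named investigator".
- Stress is given under physician and nursing supervision. Because the CT follows the PET and is to use the same agent (D.1), the patient has normally already had a clinical stress with that drug.

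All of this stands, and it limits the risk. It shows which text should win, but it does not make the two texts agree.

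A reader might infer more than the documents support:

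- *Patients with heart block will be enrolled and stressed.* Nothing suggests that such a patient would pass an all-no screen. Enrolment is unlikely.
- *The sentence is the only thing keeping hypotensive patients from beta-blockers.* It is not. The opening of E.1.a already requires that contraindications to beta-blockers be ruled out with the physician of record and permission sought. The sentence backs this up by naming hypotension.
- *The hypotension conflict is identical to the heart-block one.* That would require reading acute out of exclusion 9. Declaring non-acute cases eligible would be equally unsupported.
- *Revascularised patients will enter the study.* The PET form in section F covers imaging after intervention, so such patients can be on the schedule, but D.1 already excludes them.

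**Conclusion.** Two statements in E.1.a are wrong as written: the beta-blocker sentence on heart block, and inclusion 1 on the referral test. Both are operative eligibility rules, and in each case the rest of the protocol shows what was meant. The hypotension wording is an ambiguity for the sponsor to resolve. The missing prior-intervention item is housekeeping.

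Severity is minor to should-fix. The heart-block conflict deserves correction because it concerns a listed warning for a research-only stress, but existing checks make harm unlikely. The inclusion 1 error would bar the intended population if read literally, but it is an evident slip.

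The conclusion assumes that exclusion 10, the more protective statement, is the intended one, and that recruitment is through PET referral as four statements say. It implies no bias in the results and no defect in the sample size or the analysis.

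**What to change.** 1. **Heart block.** Delete it from the beta-blocker sentence so that exclusion 10 governs. COPD and asthma can stay, since no exclusion item contradicts them.
2. **Hypotension.** The sponsor should choose one of two wordings. (a) If every systolic pressure below 100 mm Hg is to be excluded, drop acute from exclusion 9 and remove hypotension from the sentence. (b) If only acute cases are to be excluded, say what acute means and keep the no-beta-blocker instruction for the rest. Under (a), both edits must be made together; removing hypotension from the sentence alone would lose the explicit instruction while leaving exclusion 9 unclear.
3. **Inclusion 1.** Change CT-MPI to PET-MPI.
4. **Housekeeping.** Add D.1's prior-intervention exclusion to the E.1.a list in D.1's own terms, keeping PCI and CABG as examples so that the item is no narrower than D.1. D.1's treatment-change exclusion can stay where it is: patients are approached before or on the day of the PET, so it acts mainly after enrolment.

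The cost is a short amendment: the sentence, inclusion 1 and one added item (three places), plus exclusion 9 under either hypotension option unless acute is defined elsewhere. Design, sample size and analysis do not change.

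### Section E.1.a both excludes and admits patients with second- or third-degree heart block, and does the same for acute systolic pressure below 100 mm Hg

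*Combined protocol and SAP*

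**What the plan says.** The rule at the head of the exclusion list in section E.1.a is "The presence of the following excludes subjects from the study", and every answer on the list must be no. Item 9 begins "Acute hypotension (<100 mm Hg systolic". Item 10 reads "Subject with 2nd or 3rd degree AV block" and carries no qualifier.

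Two short paragraphs follow the list. The first gives beta-blockers to patients whose heart rate is above 75 bpm. The second deals with patients who have a contraindication to beta-blockers. It names four conditions, starting with "chronic obstructive pulmonary disease, asthma sensitive to beta agonists", and ends the list by saying that patients with "second- or third-degree heart block, hypotension (<100 mm Hg systolic) are in principle eligible for participation in the study". The only handling it prescribes is "however, no beta-blockers will be used in such individuals".

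The research CT includes a pharmacological stress acquisition. Section D.1 (Pharmaceutical stress protocol) specifies a single 0.4 mg injection of regadenoson, and the Image Acquisition text requires the agent that was used at PET. Section E.1.c (Regadenoson) lists sinoatrial and AV nodal block, hypotension and bronchoconstriction among the warnings for that drug.

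**The concern.** An eligibility list should give one answer for each patient. Here a patient with high-degree AV block is ineligible under item 10 and eligible a few lines later. A patient with an acute systolic pressure below 100 mm Hg is treated the same way. Neither condition is incidental to the procedure, because each corresponds to a warning that the protocol itself gives for the stress agent. The later sentence withholds the beta-blocker and does not mention the stressor. Someone working from that sentence alone could enrol such a patient and go on to give the stressor.

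Section E.3 states that the CT is done for research and brings participants no direct benefit, so there is no clinical gain to set against an avoidable exposure.

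**Working it through.** No arithmetic beyond a count applies, and the plan gives no figure to reproduce. The check sets the four conditions in the beta-blocker sentence beside the exclusion list and the regadenoson warnings.

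| Condition in the beta-blocker sentence | Exclusion list (E.1.a) | Matching regadenoson warning (E.1.c) | Result |
|---|---|---|---|
| Second- or third-degree heart block | Item 10, unqualified | AV nodal block | Complete conflict |
| Systolic below 100 mm Hg | Item 9, same threshold, limited to acute | Hypotension | Certain conflict if acute; unclear if not |
| COPD | Not listed | Bronchoconstriction | No conflict; admitted |
| Beta-agonist-sensitive asthma | Not listed | Bronchoconstriction | No conflict; admitted |

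Conditions in conflict with an exclusion: 2 of 4. Conditions simply admitted: 4 - 2 = 2.

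**Heart block.** The condition is the same in both places and neither text limits it. If the words in principle mean subject to the exclusion list, naming heart block has no effect, because item 10 always removes the patient. If they do not mean that, the sentence overrides item 10. No reading gives both texts effect.

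**Hypotension.** The threshold is identical, but item 9 is confined to acute hypotension and the later sentence is not. For an acute low pressure the conflict is the same as for heart block. For a stable, long-standing systolic pressure below 100 mm Hg, item 9 on its wording does not exclude and the sentence admits. That is consistent, but it may not be what was intended, and the plan does not say.

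**Timing.** Item 1 ties pregnancy testing to "within 24 hours before study agent administration", which suggests that at least part of the list is meant to hold at dosing. Items 9 and 10 give no time. The CT may be up to 90 days after PET (section D.1), so a blood pressure criterion needs a stated day.

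**Any reconciling text.** None was found. Section E.2.b sets eligibility safeguards for renal function and contrast allergy, but not for conduction or blood pressure.

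**The case against.** The strongest reply is that the sentence is about beta-blockers and was never meant to widen eligibility. It follows the heart-rate rule, and its only instruction is to withhold beta-blockers. The numbered exclusions come first and all must be answered no. Under E.1.a a physician investigator determines eligibility, and the physician of record is approached only when no exclusion is present. Section E.5 adds that a named investigator confirms eligibility in each case. On this view a patient with AV block fails the checklist before the later sentence is reached, and the sentence is leftover explanatory text.

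Most of that stands. It is the more natural account of how the sentence arose, and it makes the practical risk small. A reader might infer that the plan deliberately overrides two safety exclusions, or that patients with high-degree block will be given the stressor. The documents do not support either inference. What the reply does not do is remove the conflict: it works only by treating the sentence as having no effect for these two conditions, which is a reason to delete them.

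A reader might also infer that patients with COPD or asthma receive the stressor with no written precaution. That is not supported. Sections D.1 and E.1.c require physician and nursing supervision. E.1.c names bronchoconstriction as a warning and ends the examination at first signs of side effects, immediately after a sentence on dyspnea. E.2.b provides for clinical monitoring and treatment. Item 6 ("Subject with known hypersensitivity to iodinated contrast material, beta-blockers, or pharmaceutical stressors used in this study") names the stressors too, though only for known hypersensitivity. What the text lacks is an airway-specific check before the dose and a required review of how the patient reacted at PET. The site's CT-MPI protocol (section D.1) and the Lexiscan protocol attached to the PET procedure (section F) are not reproduced and may contain both. That leaves a question to the site and no demonstrated gap.

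**Conclusion.** The eligibility text is wrong as written. The contradiction is complete for second- or third-degree heart block and certain for acute hypotension. For a non-acute systolic pressure below 100 mm Hg the plan is unclear. This is more than a clerical matter, because both conditions correspond to warnings that the protocol lists for regadenoson and the CT offers participants no direct benefit. The practical risk is nevertheless small, given physician-determined and investigator-confirmed eligibility. The documents give no prevalence for these conditions, so no number of affected patients among the planned 30 can be stated.

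The conclusion rests on the ordinary meaning of the two texts, and on heart block and AV block denoting the same condition here. It does not depend on the unreproduced site protocols. Any judgement about the handling of airway disease does depend on them, so none is made.

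**What to change.** - In the paragraph after exclusion item 10, delete heart block and hypotension (with its threshold) from the conditions described as eligible in principle. Items 9 and 10 then govern, and the sentence still does its work for COPD and asthma.
- In item 9, remove the word acute, or state that any systolic pressure below 100 mm Hg on the CT day excludes. The second form also settles the timing.
- Ask the site to confirm that its CT stress protocol requires review of the PET stress reaction and of airway status before dosing, and add a cross-reference to it in section D.1 (Pharmaceutical stress protocol).

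The cost is one phrase deleted, one item reworded and one cross-reference. The PET stress record already has to be consulted so that the agent can be matched. The downside is the possible loss of an occasional otherwise eligible patient whose blood pressure is chronically low.

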**INSTRUMENTATION & SETUP PARAMETERS:**

3D PET: 350-650 keV window

PATIENT POSITIONING: Supine with the arms placed above the patient's head. The patient should not move during acquisition.

ACQUISITION PROTOCOL

1. Start IV preferably in right hand.
2. Place 12-lead EKG electrodes for monitoring.
3. Blood pressure cuff should be positioned on the opposite arm from the IV or ankle.
4. Position patient in scanner with arms overhead
5. Start the CT scout, followed by a slow pitch rest CT attenuation scan under shallow breathing.
6. Start the Agatston scoring CT (breath hold, ECG gated)
7. Start the generator for rest Rb-82 infusion IV immediately followed by PET emission acquisition (7.5min) in list mode.
8. Inject Lexiscan 0.4 mg IV bolus over 10s followed by 5 mL saline flush. Immediately thereafter, start the generator for stress Rb-82 infusion IV as well as the PET emission acquisition (7.5 min) in list mode. Blood pressure and EKG should be monitored at one minute intervals.
9. Post-image processing for all cardiac studies is detailed below.

DATA PROCESSING:

The PET reconstruction quantitative processing is described below:

1. Calcium scoring CT, slow pitch CT, and reconstructed static rest and stress images are exported to the Leonardo workstation.
2. Technologist analyzes the fused CT and PET images to ensure proper image registration. Manufacturer-provided software will be used to correct for misalignment prior to final reconstruction of images.
3. Static images for tomographic display and gated images are reconstructed after applying a 2 min delay from start of rest and stress acquisitions. Longer delays may be needed in patients with low ejection fraction and increased blood pool activity at the discretion of the cardiac reader. OSEM iterative is used, 4 iterations, 16subsets, Gaussian post-filter 7 mm.
4. Quantitative processing is performed on the Emory Cardiac Toolbox Processing PC by a technologist with appropriate training in the used of the Toolbox. Care should be taken to complete the following sections: Parameters, Slices, Polar Maps, and Functional Analysis. Upon completion of processing a review file is automatically transferred to the reading room for physician review.

OPTIONAL MANEUVERS:

→"Stress" may be induced pharmacologically with adenosine or dipyridamole if regadenoson is not available.

RELATED DOCUMENT(S)/LINK(S):

N/A

DEFINITIONS: (If applicable)

Rubidium PET Myocardial Perfusion Imaging

2 of 3

N/A

